4.9. Changes to Protocol-Planned Analyses

No changes to the analyses specified in Protocol IMMB.

5. Sample Size Determination

See the ISA or the ISA-SAP for information on the sample size determination.

6. Supporting Documentation

6.1. Appendix 1: Demographic and Baseline Characteristics

Demographics and baseline characteristics will be summarized in the mITT population by treatment group. The summary will include descriptive statistics such as the number of participants, mean, standard deviation, median, minimum, maximum for continuous measures, and frequency counts and percentages for categorical measures. No formal statistical comparisons will be made among treatment groups.

Depending on the study design of the ISA, the ISA-SAP may specify additional analyses for characterizing the maintenance period.

The demographic and baseline characteristic variables outlined in [Table 6.1](#) will be summarized across ISAs. Table 6.1 identifies variables with *a priori* interest for subgroup analyses although ISAs are not required to report subgroup analyses; see the ISA-SAP for more information.

Table 6.1. Demographic and Baseline Characteristic Variables

Variable	Quantitative	Categorical Summary	Subgroup Analysis
Age ^a	Yes	<35, 35-<50, 50-<65, ≥65	Yes
Height	Yes		
Weight	Yes		
BMI (kg/m ²)	Yes		
Sex	No	Female, Male	Yes
Race	No		
Country	No	[Depends on ISA. Puerto Rico is included in the United States]	Yes
Prior AD treatments	No	None, Topicals (TCS, TCI, JAK inhibitors, PDE4 inhibitors), Phototherapy or Photochemotherapy, Systemic Corticosteroids, Systemic Immunosuppressives, Advanced Biologics and/or Small Molecules for AD	
vIGA-AD	No	3, 4	Yes
EASI	Yes	<20, 20-<30, ≥30	Yes
BSA	Yes		
SCORAD	Yes		
Itch NRS	Yes	<4, ≥4	Yes

Abbreviations: AD = atopic dermatitis; BMI = body mass index; BSA = body surface area; EASI = eczema area and severity index; eCRF = electronic case report form; JAK = Janus kinase; NRS = numeric rating scale; PDE4 = phosphodiesterase-4; SCORAD = SCORing atopic dermatitis; TCI = topical calcineurin inhibitors; TCS = topical corticosteroids; vIGA-AD = validated Investigator Global Assessment for Atopic Dermatitis.

^a Age will be calculated using an imputed date of birth of July 1st in the year of birth collected in the eCRF. It will be calculated as: Age (in years) = (date of first dose – imputed date of birth) / 365.25.

6.2. Appendix 2: Definition of Efficacy Endpoints and Patient-Reported Health Outcomes

Table 6.2 provides the derivation of efficacy and patient-reported health outcomes common across the ISAs. The ISA-SAP will provide additional derivations for ISA-specific outcomes (for example, the asthma control questionnaire in Study J4E-MC-FR01).

Table 6.2. Derivation of Efficacy and Patient-Reported Health Outcomes

Measure	Variable	Derivation / Comment	Approach if Missing Components
vIGA-AD	vIGA-AD Score	Single item in integers from 0 to 4: 
• 0 represents 'clear'• 4 represents 'severe'	--
	vIGA-AD of 0 or 1	Observed score of 0 or 1.	--
EASI	EASI Score	Derive EASI region score for each of head and neck, trunk, upper limbs, and lower limbs as follows: $EASI_{region} = (\text{erythema} + \text{edema/papulation} + \text{excoriation} + \text{lichenification}) * (\text{value from percentage involvement})$, where erythema, edema/papulation, excoriation, and lichenification are evaluated on a scale of 0 to 3 and value from percentage involvement is on a scale of 0 to 6. Total EASI score is: $EASI = 0.1*EASI_{head and neck} + 0.3*EASI_{trunk} + 0.2*EASI_{upper limbs} + 0.4*EASI_{lower limbs}$	If value from percentage involvement is 0, then corresponding EASI region score is 0 even if erythema, edema/papulation, excoriation, and/or lichenification are missing. Otherwise, EASI score is missing if any component is missing.
	Change from baseline	Observed EASI score – baseline EASI score	Missing if baseline or observed is missing.
	Percent change from baseline	$100 \times \frac{\text{Observed score} - \text{Baseline}}{\text{Baseline}}$	Missing if baseline or observed is missing.
	EASI-XX For XX = 50, 75, and 90	% change from baseline \leq XX	Missing if baseline or observed is missing.
SCORAD	SCORAD score	$SCORAD = A/5 + 7B/2 + C$, where A is extent of disease, range 0-100 B is disease severity, range 0-18 C is subjective symptoms, range 0-20	Missing if component A, B, and/or C are missing.
	Change from baseline	Observed SCORAD score – baseline SCORAD score	Missing if baseline or observed is missing.
	Percent change from baseline	$100 \times \frac{\text{Observed score} - \text{Baseline}}{\text{Baseline}}$	Missing if baseline or observed is missing.
	SCORAD-XX For XX = 50, 75, and 90	% change from baseline \leq XX	Missing if baseline or observed value is missing.

Measure	Variable	Derivation / Comment	Approach if Missing Components
Itch NRS	Itch NRS Score	The (prorated) mean based on the prior 7 days. For example, if a participant only had 3 days, then the itch NRS score is the mean of the 3 non-missing days, range 0-10. The ISA-SAP maps the daily dairy entries to study visits.	Baseline: Missing if more than 3 days from prior week are missing. Post-Baseline: Missing if all days from prior week are missing.
	Change from baseline	Observed itch NRS score – baseline itch NRS score	Missing if baseline or observed value is missing.
	4-point improvement	Change from baseline ≤ -4	Missing if baseline or observed value is missing
Skin Pain NRS	Skin Pain NRS Score	The (prorated) mean based on the prior 7 days. For example, if a participant only had 3 days, then the skin pain NRS score is the mean of the 3 non-missing days, range 0-10. The ISA-SAP maps the daily dairy entries to study visits.	Baseline: Missing if more than 3 days from prior week are missing. Post-Baseline: Missing if all days from prior week are missing.
	Change from baseline	Observed skin pain NRS score – baseline skin pain NRS score	Missing if baseline or observed value is missing.
	4-point improvement	Change from baseline ≤ -4	Missing if baseline or observed value is missing.
POEM	POEM score	Sum of questions 1 to 7, range 0-28.	Missing if all questions are left unanswered. Otherwise, a prorated mean is used: mean score of answered questions times 7. If more than one response is selected, the response with the highest score is used.
	Change from baseline	Observed POEM score – baseline POEM score	Missing if baseline or observed value is missing.

Measure	Variable	Derivation / Comment	Approach if Missing Components
	4-point improvement	Change from baseline ≤ -4	Missing if baseline or observed value is missing
DLQI	DLQI total score	A DLQI total score is calculated by summing all 10 question responses, range 0-30.	Missing if any question is unanswered. Note: For questions 3-10, 'Not relevant' is scored as a 0.
	Change from baseline	Observed DLQI total score – baseline DLQI total score	Missing if baseline or observed is missing.
	4-point improvement	Change from baseline ≤ -4	Missing if baseline or observed value is missing.
ADCT	ADCT score	Sum of questions 1 to 6, range 0-24.	Missing if any question is left unanswered.
	ADCT ≥ 7 (Not in control)	Observed ADCT score ≥ 7	--
	Change from baseline	Observed ADCT score – baseline ADCT score	Missing if baseline or observed value is missing.
	5-point improvement	Change from baseline ≤ -5	Missing if baseline or observed value is missing.

Abbreviations: ADCT = Atopic Dermatitis Control Tool; DLQI = Dermatology life quality index; EASI = eczema area and severity index; ISA-SAP = intervention specific appendix-statistical analysis plan; NRS = numeric rating scale; POEM = Patient-Oriented eczema measure; SCORAD = SCORing atopic dermatitis; vIGA-AD = validated Investigator Global Assessment for Atopic Dermatitis.

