4.2. Scientific Rationale for Study Design

EASI-75 as the primary endpoint measure

The EASI and SCORAD are both regarded as acceptable instruments to measure the clinical signs of AD (Schmitt et al. 2013). Study FR01 uses a 75% reduction relative to the baseline EASI score (EASI-75) as the primary measure of efficacy. The EASI is a validated measure used in clinical practice and clinical trials to assess the severity and extent of AD (Hanifin et al. 2001).

Duration of treatment period and posttreatment follow-up

The duration of the induction period (16 weeks) and the primary endpoint at Week 16 is based on previous clinical trials of systemic therapies in AD (Simpson et al. 2016). The remaining duration of the study is intended to allow exploratory assessments of various LY3454738

maintenance dosing regimens. To reduce participant burden, topical rescue medication is permitted under certain circumstances (Section 6.9.1).

The posttreatment follow-up period allows for continued monitoring of safety and maintenance of response after the last dose. The duration of this period is considered sufficient to wash out LY3454738 based on the half-life of the **CCI** mg dose, **CCI**

CCI

Appropriateness of study population

The study inclusion criteria will enable enrollment of patients who are representative of the general population with moderate-to-severe AD. The EASI score ≥ 16 , IGA score ≥ 3 , and $\geq 10\%$ of BSA involvement at baseline have been used as inclusion criteria in other studies of AD (Simpson et al. 2016).

Choice of placebo control, number of treatment groups, and escape arm

A double-blind, placebo-controlled design limits bias for the participant assessments and investigator assessments and enables a clearer interpretation of the effects of the active study intervention.

The multiple dosing regimens enable an evaluation of safety and efficacy across several doses and frequencies, thereby providing information to guide the selection of dosing regimens for future studies.

The maintenance “escape arm” for nonresponders gives participants an opportunity to remain in the study and receive potential benefit from a higher dose.

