9.3. Statistical Analyses

9.3.1. General Considerations

Statistical analysis of this study will be the responsibility of the sponsor or its designee. All statistical tests, unless otherwise noted, will be 2-sided and will be performed at a significance level of 0.05. Unless indicated otherwise in the ISA-SAP, the analyses will be conducted as described in this section.

Changes to the data analysis methods

Any change to the data analysis methods described in this ISA will require an amendment only if the change affects a principal feature of the ISA. Any other change to the data analysis methods described in the ISA and the justification for making the change will be described in the CSR. Additional exploratory analyses of the data will be conducted as deemed appropriate. Complete details of the planned analyses will be documented in the ISA-SAP.

Summary of data

Continuous data will be summarized in terms of mean, standard deviation, minimum, maximum, median, and number of observations. Categorical data will be summarized as frequency counts and percentage. Comparison between each LY3454738 dosing regimen and placebo will be performed for all efficacy and patient-reported endpoint analyses during the induction period with no adjustment for multiple comparisons.

Induction dose selection

Dose selection at the end of the induction period will be based on comparisons between each regimen and placebo using dose-response modeling. Dose selection rules and specifics will be detailed in the ISA-SAP.

Baseline definition

For efficacy and PRO analyses, baseline will be defined as the last available value before the first dose of study intervention. In most cases, this value will be what is recorded at the randomization visit (Visit 0). For efficacy measures, if a participant does not take any study intervention, the last available value on or prior to randomization date will be used. Change from baseline will be calculated as the visit value of interest minus the baseline value.

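### SAP Table 6.2 omits the minus sign from the EASI-XX and SCORAD-XX responder rules, so the printed EASI-75 rule counts unchanged and worsened participants as responders

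*SAP*

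**What the plan says.** SAP Appendix 2 (Section 6.2) sets its own scope: "Table 6.2 provides the derivation of efficacy and patient-reported health outcomes common across the ISAs". It leaves to the ISA-SAP only extra derivations for outcomes specific to one ISA, with the FR01 asthma questionnaire as the example. EASI is not such an outcome.

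Within Table 6.2:

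- Change in EASI and SCORAD is the observed score minus the baseline score. Percent change is 100 × (observed − baseline)/baseline.
- The row "EASI-XX For XX = 50, 75, and 90" gives the responder rule as percent "change from baseline \leq XX".
- The row "SCORAD-XX For XX = 50, 75, and 90" gives the same rule.
- The 4-point improvement rows for Itch NRS, Skin Pain NRS, POEM and DLQI read "Change from baseline ≤ -4". The 5-point ADCT row reads "Change from baseline ≤ -5".

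In the protocol, Section 4.2 states: "Study FR01 uses a 75% reduction relative to the baseline EASI score (EASI-75) as the primary measure of efficacy". Section 9.3.1 fixes the sign: "Change from baseline will be calculated as the visit value of interest minus the baseline value". The abbreviation list (Attachment 8) likewise describes EASI-75 and SCORAD-75 as reductions from baseline. Section 9.3.2 makes the proportion achieving EASI-75 at Week 16 the primary comparison and counts participants with intercurrent events of interest before Week 16 as nonresponders.

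**The concern.** With change taken as observed minus baseline, a 75% improvement is a percent change of −75. A responder rule of ≤ 75 then admits everyone except those who worsen by more than 75%. The five other change-based responder rows in the table carry the minus sign, and these two do not.

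The primary endpoint is at stake. If the row were programmed as printed, an event-free participant with a Week 16 score would be a nonresponder only after worsening by more than 75%. Because intercurrent events already count as nonresponse, the comparison between arms would then mainly measure differences in rescue use, prohibited medication and discontinuation rather than improvement in EASI. The nested endpoints would also run in the wrong order, with EASI-90 the most lenient.

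**Working it through.** The plan states no figure for this rule, so there is none to reproduce. The check applies the table's own formula.

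**Inputs**

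- Percent change = 100 × (observed − baseline)/baseline (SAP Table 6.2).
- XX = 50, 75, 90 (SAP Table 6.2).
- Eligibility floor: baseline EASI 16 (Protocol 5.1).
- EASI components: four signs scored 0–3, area value 0–6, region weights 0.1, 0.3, 0.2, 0.4 (SAP Table 6.2).
- SCORAD = A/5 + 7B/2 + C, with maxima 100, 18 and 20 (SAP Table 6.2).

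**Step 1: cutoffs.** Solving for the observed score:

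- intended rule (percent change ≤ −XX): observed ≤ baseline × (1 − XX/100);
- printed rule (percent change ≤ XX): observed ≤ baseline × (1 + XX/100).

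At baseline EASI 16:

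| Endpoint | Intended cutoff | Printed cutoff |
|---|---|---|
| EASI-50 | 16 × 0.50 = 8 | 16 × 1.50 = 24 |
| EASI-75 | 16 × 0.25 = 4 | 16 × 1.75 = 28 |
| EASI-90 | 16 × 0.10 = 1.6 | 16 × 1.90 = 30.4 |

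Under the printed rule a participant who stays at 16 (0%) or rises to 28 (+75%) is an EASI-75 responder.

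**Step 2: ordering.** At baseline 20, an observed score of 36 is a change of 100 × (36 − 20)/20 = +80%. The printed rules make this participant an EASI-90 responder but not an EASI-75 or EASI-50 responder. Under ≤ −XX the order is correct: a score of 5 (−75%) meets EASI-50 and EASI-75 but not EASI-90.

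**Step 3: ceiling.** Maximum EASI = (0.1 + 0.3 + 0.2 + 0.4) × (4 × 3 × 6) = 72. The printed EASI-75 cutoff exceeds 72 once baseline is above 72/1.75 = 41.1. From there every possible score is a response. For SCORAD the maximum is 100/5 + 7 × 18/2 + 20 = 103, and the same happens above 103/1.75 = 58.9.

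**Step 4: treatment difference.** The documents do not determine this.

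- The printed rule includes every true responder. With the planning rates in Protocol 9.5 (52% and 12%, for a participant group whose description is redacted), the literal rates lie in 52–100% on LY3454738 and 12–100% on placebo.
- The difference is therefore bounded only by 52 − 100 = −48 and 100 − 12 = +88 points, which says little.
- The mechanism shows more clearly by assumption. Suppose every event-free participant has a Week 16 score and none worsens by more than 75%. The literal rate in each arm is then its event-free proportion. Assumed proportions of 90% and 90% give a difference of 0; 90% and 70% give 20 points, whatever the true effect on EASI. These proportions are illustrations and do not come from the plan.

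**The case against.** Four points can be made on the other side.

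1. **The sign may have been lost in text extraction.** The two XX cells carry formula mark-up for the inequality, while the ≤ −4 and ≤ −5 rows are plain characters, so the sign surviving there says little about these cells. The minus signs that did survive as formula text are subtractions inside a longer expression, and the two XX cells have identical wording. This stands: the original file has to be checked first. Against it, the percent-change formulas carry the same kind of mark-up and kept their minus, and the loss would have to affect both XX rows and no other row.

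2. **The intent is obvious.** The protocol fixes the meaning, the 52% and 12% planning rates make sense only for a reduction, and the literal rule defeats itself because EASI-90 becomes the easiest endpoint. This is right. It makes literal programming unlikely, but it does not make the written definition correct.

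3. **The governing document is elsewhere.** The SAP supplied is the master-protocol SAP, approved 15-Aug-2023, before Amendment (b) of 12-Sep-2023 changed the primary estimand. SAP Sections 4 and 4.3 send the primary analysis to the ISA-SAP, which is not among the documents. This limits the likely consequence. A correct ISA-SAP would still leave two documents in conflict on the primary endpoint.

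4. **The effect on the treatment difference is speculative.** The bound is uninformative and the event-free proportions are assumed. This also stands. The argument rests on the cutoffs (4 versus 28), which need no assumption.

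**Conclusion.** The concern holds. In the text supplied, the EASI-XX and SCORAD-XX rules in Table 6.2 are wrong by a minus sign, and following them literally gives a wrong primary endpoint. At baseline 16 the EASI-75 cutoff moves from 4 to 28, and above a baseline of 41.1 the criterion excludes nobody. These figures follow from the table's own formulas. The consequence for the trial result cannot be sized: it depends on whether the row was programmed literally, on the event-free proportions in each arm, and on how many participants worsen by more than 75%.

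This is most plausibly a typographical slip and not a deliberate redefinition: SAP Section 4.9 declares no changes to the analyses in Protocol IMMB. It still has to be corrected, because it sits in the stated derivation of the primary endpoint. The conclusion is conditional on the original file also lacking the sign.

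**What to change.** 1. Check both rows in the original SAP file.
2. If the sign is absent there, change the EASI-XX and SCORAD-XX rules to percent change from baseline ≤ −XX, or equivalently percent improvement ≥ XX.
3. Before unblinding, confirm that the FR01 ISA-SAP and the programming specifications use the same rule. A simple test case is baseline 20: a score of 5 must be an EASI-75 responder, and scores of 10, 20 and 35 must not.

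The cost is one character in each of two rows, plus the document check. Visits, data collection and sample size are unaffected.

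### SAP Table 6.2 sets no minimum number of answered POEM items, so in extreme cases one answer stands for all seven and can create or hide a 4-point responder

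*SAP*

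**What the plan says.** SAP section 6.2 (Appendix 2), Table 6.2, defines the POEM total as "Sum of questions 1 to 7, range 0-28". Its missing-component rule is "Missing if all questions are left unanswered. Otherwise, a prorated mean is used: mean score of answered questions times 7". The same cell also covers questions with more than one response marked, so it expects imperfect forms.

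Change is "Observed POEM score – baseline POEM score", and the 4-point improvement is "Change from baseline ≤ -4". Neither entry asks for the same items to be answered at the two visits.

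Other rows of the table handle incomplete data differently:

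- DLQI: "Missing if any question is unanswered".
- ADCT: "Missing if any question is left unanswered".
- Itch and skin pain NRS at baseline: "Baseline: Missing if more than 3 days from prior week are missing", so at least 4 of 7 diary days are needed. After baseline these two scores are missing only if every day is missing, so 1 of 7 days is enough.

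On scope, the section states that "Table 6.2 provides the derivation of efficacy and patient-reported health outcomes common across the ISAs". It leaves to the ISA-SAP the extra derivations for outcomes specific to one ISA. In FR01 the POEM appears among the electronic patient-reported outcomes in the Schedule of Activities (Protocol section 1.3, Tables 1 and 2). Protocol section 9.3.1 plans comparisons of each regimen with placebo on all patient-reported endpoints during induction.

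**The concern.** Scaling up a mean over answered items is reasonable when most items are present. With no floor, one answered question stands in for all seven. The total is then coarse, and the change score can set one symptom at follow-up against a different set at baseline. The responder flag is the most exposed variable, because its 4-point cut is smaller than the jump a one-item form can produce.

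Two things are at stake. Responder status on sparse forms may reflect which questions were answered rather than any change in the disease. A nearly blank form also counts as an observed score, so it would not trigger the handling of missing data that Protocol section 9.3.1 defers to the ISA-SAP.

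**Working it through.** **Inputs.** From Table 6.2: 7 items, total 0–28, score = 7 × (sum of answered items ÷ k) when k items are answered, responder if change ≤ −4. Inferred, not stated: each item scores 0–4 in whole numbers, since 28 ÷ 7 = 4. This reproduces the stated range: 7 × 0 = 0 and 7 × 4 = 28.

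**Step 1: same k items answered at both visits.** A one-category change on one item moves the total by 7/k. The number of category steps needed for a response is 4 ÷ (7/k), rounded up.

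| Items answered (k) | One-category step (7/k) | Meets ≤ −4 alone? | Category steps needed |
|---|---|---|---|
| 1 | 7.00 | yes | 1 |
| 2 | 3.50 | no | 2 |
| 3 | 2.33 | no | 2 |
| 4 | 1.75 | no | 3 |
| 5 | 1.40 | no | 3 |
| 6 | 1.17 | no | 4 |
| 7 | 1.00 | no | 4 |

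With k = 1 the only possible totals are 0, 7, 14, 21 and 28, so any fall is at least 7 points. The one-step response exists only in this row.

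**Step 2: complete baseline, one item answered later.** Take baseline items 4, 4, 4, 2, 2, 1, 1, total 18.

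- Nothing has changed and only an item scored 2 is answered: 7 × 2 = 14, and 14 − 18 = −4. This is a responder with no improvement.
- Nothing has changed and only an item scored 4 is answered: 7 × 4 = 28, and 28 − 18 = +10.
- Every item has fallen by one category (not below 0): true follow-up 3 + 3 + 3 + 1 + 1 + 0 + 0 = 11, true change 11 − 18 = −7, a responder. If only an item now scored 3 is answered: 7 × 3 = 21, and 21 − 18 = +3. The responder is hidden.

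**Step 3: how much more often would a sparse form give a false responder?** The documents give no item-level data, so this rests on assumptions. Suppose there is no true change, the same items are answered at both visits, and each item falls one category with probability q, rises one with probability q, and otherwise stays.

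With q = 0.2 and independent items, P(change ≤ −4) for k = 1 to 7 is 20.0, 4.0, 8.0, 2.1, 3.6, 1.0 and 1.7%. For example, k = 1 gives 0.2, and k = 2 needs both items to fall, 0.2² = 0.04. The series is not monotone, because 7/k falls unevenly against the cut of 4.

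| Assumption | One item | Seven items | Ratio |
|---|---|---|---|
| q = 0.1, independent | 10.0% | 0.2% | about 50 |
| q = 0.2, independent | 20.0% | 1.65% | about 12 |
| q = 0.2, latent item correlation 0.3 | 20.0% | about 9% | about 2.2 |
| q = 0.2, latent item correlation 0.5 | 20.0% | 13.5% | about 1.5 |
| q = 0.2, latent item correlation 0.7 | 20.0% | 16.7% | about 1.2 |

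The ratio runs from about 1.2 to about 50 according to inputs that the documents do not give.

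**The case against.** The strongest case against is that this is a corner case on a lesser outcome.

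- **Narrow condition.** A reader might infer that any one-category change on one item makes a POEM responder. That is not so. It needs the same single item to be the only answer at both visits, and it fails once two items are answered. This stands, and the point is limited accordingly. The different-items problem in Step 2 is separate and does not need a sparse baseline.
- **Size.** A reader might take the 12-fold ratio as the size of the effect. It rests on independence between seven symptom items reported by one person about one disease, which nothing in the documents supports. It should not be quoted as a magnitude.
- **Selective comparison.** A reader might also infer that the table contradicts itself. It sets rules instrument by instrument, and the post-baseline NRS rows are as lenient as the POEM row. That weakens any charge of inconsistency. It does not justify the POEM rule, because several days' ratings of one symptom are closer substitutes for each other than seven different questions are.
- **Materiality.** The POEM is electronic in FR01, the primary endpoint is EASI-75 at Week 16, no multiplicity-controlled claim depends on the POEM, and Protocol section 9.3.1 expects little missing data after intercurrent events. The ISA-SAP, which was not supplied, could add a floor. All this limits the impact. However, the documents do not say that skipping a question is blocked, and the cell itself provides for unanswered ones.

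**Conclusion.** The point holds as a minor one. Table 6.2 allows a POEM total from a single answer. In the extreme case one category step on that answer is a 7-point change and a response, where a full form needs four steps. When the answered items differ between visits, a responder can be created without improvement or hidden despite it. These results follow from the stated rule, given items scored 0–4.

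The frequency and net effect on any treatment comparison cannot be stated from the documents. The effect in FR01 is probably small. Nothing supplied supports reading this as a threat to the primary analysis or as bias in favour of either arm.

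**What to change.** Change the POEM missing-components cell in SAP Table 6.2 to: score missing if fewer than 4 of the 7 items are answered; otherwise 7 × the mean of the answered items. Keep the rule for multiply marked items. Make the change before unblinding.

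Four of seven is the floor that the table already uses for baseline itch and skin pain NRS. It caps a one-category step on one item at 7 ÷ 4 = 1.75 points.

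The cost is one table cell and a few more missing POEM scores, which then fall under the ISA-SAP's missing-data rule.

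The floor reduces the problem of different items but does not remove it. In the Step 2 example, answering only the four lowest items unchanged gives 7 × (2 + 2 + 1 + 1) ÷ 4 = 10.5, a change of 10.5 − 18 = −7.5. Requiring all seven items, as for the DLQI and ADCT, would remove it at the price of more missing scores. If the sponsor expects almost no skipped items, either choice costs very little.
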